5.0 OBJECTIVES AND ENDPOINTS

Primary Objectives	Primary Endpoints

To compare the progression free survival (PFS) of patients treated with CB-839 + everolimus (CBE) versus placebo + everolimus (PboE) for advanced or metastatic clear cell RCC (ccRCC) previously treated with
 
 • At least 2 lines of therapy, including at least one vascular endothelial growth factor (VEGFR) tyrosine kinase inhibitor (TKI) • Radiographic progression of mRCC must have occurred (per investigator assessment) on or after the most recent systemic therapy and within 6 mo prior to C1D1. 	Investigator-assessed PFS per Response Evaluation Criteria in Solid Tumors (RECIST) v1.1
Secondary Objectives	Secondary Endpoints
To compare the overall survival (OS) of study patients treated with CBE vs. PboE	Assessed by time from randomization to death by any cause
Additional Objectives	Additional Endpoints
To compare the objective response rate (ORR), Duration of Response (DOR), and Disease Control Rate (DCR) of CBE vs. PboE	Per RECIST v1.1
To compare the safety and tolerability of CBE vs. PboE	Assessed by type, incidence, severity, seriousness, and study drug-relatedness of adverse events
To investigate the population pharmacokinetics (PK) of CB-839	Analysis of any potential relationship between drug exposure and various population parameters using sparse PK sampling
To investigate the relationship of genetic variants and response to CBE vs. PboE	Genetic variants and other biomarkers related to mTOR, angiogenesis, and metabolic pathways
Change in kidney-cancer related symptoms	Functional Assessment of Cancer Therapy-Kidney Cancer Symptom Index (FKSI-19)
Change in mobility, self-care, usual activities, pain/discomfort, and anxiety/depression, and global health	EuroQol Health questionnaire instrument (EQ-5D-5L)

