14.5 Sample Size Estimation

A median PFS of 3.7 mo is estimated for the everolimus control group based on published data for 3rd line treatment of advanced ccRCC. The published data include non-randomized everolimus-specific PFS ([Heng 2015](#)), PFS across the 3rd line setting for all commonly used

agents (ibid.), and results from a Phase 3 randomized 3rd line study of dovitinib vs. sorafenib (GOLD study, [Motzer 2014](#)). In total across the IMDC database and the randomized GOLD study, these data represent 1490 unique patient outcomes specific to the 3rd line setting.

The proposed study of CBE vs. PboE will enroll patients with a 2:1 randomization between experimental and control arms with an accrual period of 8 mo and additional follow-up of 6 mo. If the control arm PFS is 3.7 mo and the true PFS hazard ratio of experimental patients to control patients is 0.60, the study will require approximately 42 experimental patients and 21 control patients in order to reject the null hypothesis of equal PFS between the two treatment arms with a power of 0.80. This estimation assumes a 1-sided type I error rate of 0.2, uniform accrual, exponential PFS distributions and the log-rank test for PFS comparison. The expected total PFS event count is 48 under the above assumptions.

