## **6.2 Determination of Sample Size**

A median PFS of 3.7 months is estimated for the everolimus control group based on published data for 3rd line treatment of advanced ccRCC (7). The proposed study of CBE vs. PboE will enroll approximately 63 patients with a 2:1 randomization between experimental and control arms with an accrual period of 8 months and additional follow-up of 6 months. If the control arm's median PFS is 3.7 months and the true PFS hazard ratio of experimental patients to control patients is 0.60, the study will require approximately 48 PFS events in order to reject the null hypothesis of equal PFS between the two treatment arms with a power of 0.80 and 1-sided type I error rate of 0.2 (exponential PFS distribution and log-rank test for PFS comparison).

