### **8.6.1 Exposure of Study Medication**

Study drug exposure statuses, which include treatment duration, total dose received (mg), number of cycles, dose intensity (mg/day), and relative dose intensity (%), will be summarized for each treatment arm for the Safety population.

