### **8.6.2 Adverse Events**

Verbatim description of AEs will be mapped to Medical Dictionary for Regulatory Activities (MedDRA, v19.1) preferred terms and system organ classes, and graded by the investigator according to NCI CTCAE v4.03. Treatment-emergent adverse events (TEAEs) will be summarized by mapped term, appropriate thesaurus level, NCI CTCAE grade, and treatment arm. In addition, serious adverse events, severe adverse events (Grade  $\geq 3$ ), and adverse events leading to study drug discontinuation or interruption will be summarized accordingly. Multiple occurrences of the same event will be counted once at the maximum grade. All deaths are reported as SAEs per study conduct. In order to accurately summarize the true SAE rate, all SAE summaries will not count grade 5 events for patients who died due to progressive disease.

For reporting purposes, “treatment emergent” is defined as adverse events occurring on or after the first dose of study drug is administered until the clinical cutoff date, or existing events that worsened after the first dose during the study.

All listings of adverse events will also include all adverse events.

Deaths reported during the study treatment period and the follow-up period after treatment completion and/or discontinuation will be listed by treatment arm.

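### AEs are compared by crude patient incidence only, although AE observation time depends on progression: if CBE works as assumed, equal AE rates would show as a modest spurious excess on CBE

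*SAP*

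**What the plan says.** Protocol 5.0 lists among the additional objectives "To compare the safety and tolerability of CBE vs. PboE". Protocol 14.4 meets it by tabulating the number and proportion of patients with each AE, by arm and worst severity. SAP 8.6.2 summarizes treatment-emergent AEs by term, CTCAE grade and arm, and states that "Multiple occurrences of the same event will be counted once at the maximum grade". Neither document plans an exposure-adjusted rate, a time-to-first-event analysis or incidence within a fixed window.

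Exposure is handled separately. SAP 8.6.1 lists treatment duration, number of cycles, total dose and dose intensity, which "will be summarized for each treatment arm for the Safety population". Nothing links these to the AE tables.

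Three further provisions determine how long a patient is observed for AEs:

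- Treatment continues until progression or unacceptable toxicity (Protocol 7.0).
- AEs are recorded from first dose to 28 days after the last dose (Protocol 10.6), or until a new treatment starts if that is earlier (Protocol 15.2).
- SAP 8.6.2 nevertheless defines treatment-emergent as running to the clinical cutoff date.

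**The concern.** The proportion of patients with at least one event rises with time under observation as well as with the underlying rate. Here that time is tied to the primary endpoint: a patient who progresses later stays on treatment and in AE collection for longer. The planned tables therefore mix toxicity with efficacy. If CBE delays progression, its crude percentages rise even when its monthly AE rate equals that of PboE. If CBE is stopped more often for toxicity, the shorter observation works the other way and could hide an excess.

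What is at stake is how the add-on toxicity of CB-839 is read. The arm-level exposure table would show that durations differ, but it does not give time at risk to first event for any term, grade or seriousness category, so a reader could not correct the AE tables from it.

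**Working it through.** **Design inputs.** Protocol 14.5: "A median PFS of 3.7 mo is estimated for the everolimus control group", "1-sided type I error rate of 0.2", "with a power of 0.80", 42 versus 21 patients, 8 months' accrual plus 6 months' follow-up. SAP 6.2: "true PFS hazard ratio of experimental patients to control patients is 0.60" and "exponential PFS distribution and log-rank test for PFS comparison". SAP 6.3 places the primary analysis about 20 months after first randomization.

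**The plan's own figure.** Schoenfeld events = (0.8416 + 0.8416)² / [(2/3)(1/3)(ln 0.60)²] = 48.86, against the stated 48. The inputs are read correctly.

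**Progression hazards.** PboE: ln 2/3.7 = 0.187 per month. CBE: 0.60 × 0.187 = 0.112 per month, median 3.7/0.60 = 6.17 months.

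**Assumptions the documents do not give.** Treatment time equals PFS time; accrual is uniform; the AE hazard r is constant and the same in both arms, varied from 0.02 to 0.50 per month; the 20 months split as 14+6 or 8+12.

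**Observation window.** Let w = 28/30.4375 = 0.92 month, u = time from randomization to data cutoff, and μ = the progression hazard. The window is the smaller of treatment time + w and u, so

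- mean window given u = w + [1 − exp(−μ(u − w))]/μ
- crude incidence = 1 − average of exp(−r × window), averaged over treatment time and over u.

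Hand check at u = 10 months, the middle of the 8+6 range. PboE: 0.92 + (1 − 0.183)/0.187 = 5.28. CBE: 0.92 + (1 − 0.360)/0.112 = 6.61. The ratio is 1.25. (Divisions use unrounded hazards.)

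**Results, averaged over u, 28-day window included:**

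| Accrual + follow-up (months) | Mean treatment time, PboE / CBE (ratio) | Mean AE window, PboE / CBE (ratio) | Crude incidence at r = 0.1, PboE vs CBE | Crude RR, r = 0.02 to 0.50 |
|---|---|---|---|---|
| 8+6 | 4.44 / 5.91 (1.33) | 5.19 / 6.50 (1.25) | 37.6% vs 44.7% | 1.24 to 1.07 |
| 14+6 | 4.72 / 6.61 (1.40) | 5.53 / 7.28 (1.32) | 38.7% vs 47.1% | 1.29 to 1.07 |
| 8+12 | 5.05 / 7.37 (1.46) | 5.91 / 8.13 (1.38) | 40.0% vs 49.8% | 1.34 to 1.07 |

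The true rate ratio is 1.0 in every cell. The largest absolute gap is about 10 percentage points.

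**Sensitivity.** Equal extra stopping hazards of 0 to 0.06 per month in both arms give RRs of 1.06 to 1.34. Removing the 28-day tail altogether, as if new treatment began at once, gives 1.11 to 1.43.

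**When it vanishes or reverses.** Under the null the two windows are equal. Under the alternative, an extra stopping hazard on CBE alone of 0.187 − 0.112 = 0.075 per month would close the gap; a larger one would reverse it.

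**Early-onset events.** With an identical hazard of 0.3 per month in month 1 only and none afterwards, crude incidence is 25.9% in both arms (RR 1.00). First events per patient-month, however, give ratios of 0.80 (8+6), 0.77 (14+6) and 0.73 (8+12).

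**The case against.** The strongest case against the point has four parts.

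- **The size is easily overstated.** A reader might infer from 6.17/3.7 = 1.67 that the design expects treatment on CBE to last 1.67 times as long. It does not say so. That is the ratio of assumed median PFS under the alternative; neither document states an expected treatment duration, treatment also stops for toxicity, and follow-up is cut off. Ignoring the cutoff and the 28-day window would give 0.1/(0.1 + 0.187) = 35% versus 0.1/(0.1 + 0.112) = 47% at r = 0.1, which is wider than the planned schedule supports. This objection stands, and the figures here allow for it.
- **Sampling error is larger.** With 21 and 42 patients, the 95% Wald half-width around 37.6% versus 44.7% is 1.96 × √(0.376 × 0.624/21 + 0.447 × 0.553/42) = 26 points, against a bias of 7. No AE test or safety decision rule is planned. This limits the importance of the point, but the bias runs in one direction across all constant-hazard events and does not average out over the tables.
- **A person-time rate can mislead in the other direction.** It assumes a roughly constant hazard. Protocol 9.5 reports, anecdotally, that the ocular events related to CB-839 become less frequent with extended dosing. In the early-onset example above, the rate ratio makes CBE look 20% to 27% safer when the hazards are identical. This stands and shapes the fix.
- **Exposure is already tabulated, and counting a patient once is not the fault.** Both are true. A first-event rate also counts each patient once. What is missing is any measure with time at risk in it, and an arm-level duration summary does not supply that.

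**Conclusion.** The point holds as a modest gap in the safety analysis. Crude incidence is the only planned between-arm AE measure, and it depends on observation time that the primary endpoint drives. If the hazard ratio is 0.60 and AE hazards are constant and equal, mean AE observation on CBE is about 1.25 to 1.38 times that on PboE, and the crude RR is about 1.07 to 1.34, smallest for common events.

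These figures rest on assumed AE rates, exponential treatment time equal to PFS, no difference in toxicity stops, and an assumed split of the 20 months. The documents do not support reading the point as a 1.67-fold exposure difference, as a bias that exists whatever the treatment effect, or as one that affects all AEs alike. Nothing in it touches the primary analysis.

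**What to change.** Keep the crude tables. For key treatment-emergent AEs, Grade 3 or higher AEs, SAEs and AEs leading to discontinuation, add to SAP 8.6.2:

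1. **A definition of time at risk:** first dose to the earliest of first event, 28 days after last dose, start of new anticancer therapy, death or data cutoff. Align the treatment-emergent definition, which now runs to clinical cutoff, with the period in which AEs are actually collected. This has to be settled first, because the denominator depends on it.
2. **A between-arm summary that uses it:** cumulative incidence of first event read at prespecified times, or incidence in a prespecified early window. In the cumulative incidence, treat death without the event as competing and the end of AE observation as censoring. Treating the end of treatment as a competing event would largely reproduce the crude percentages.
3. **First events per patient-month,** with the rate ratio and confidence interval, shown beside item 2 and not alone.

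The cost is a few extra tables from data already collected, plus the work of settling the window. Two limits should be stated in the SAP: the rate ratio assumes a roughly constant hazard and would understate CBE toxicity for early-onset events, and censoring at the end of AE observation may be informative. With 63 patients, all of this is descriptive.

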10.6 Procedure Details

This section describes assessments to be performed and recorded in the EDC.

Routine safety and tolerability will be evaluated from the results of reported signs and symptoms, scheduled physical examinations, vital sign measurements, 12-lead ECGs (including QTcF intervals), and clinical laboratory test results.

After randomization, safety assessments will be performed on day 1 of every cycle for the first 12 cycles. Starting with cycle 13, safety assessments will be performed on day 1 of every 3 cycles. More frequent safety evaluations may be performed if clinically indicated or at the

discretion of the Investigator. Unscheduled visits may be performed at any time and all should be recorded in the EDC. All AEs will be recorded from the time the patient receives the first dose of study drug up to 28 days after the last dose.

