15.2 Recording and Reporting

After informed consent, but prior to initiation of study drug, only SAEs caused by protocol-mandated interventions (i.e., a protocol-related SAE such as a biopsy) will be collected.

Patients will be followed for AEs or SAEs from the time the patient initiates treatment with the study regimen up to 28 days after the last dose or until the start of a new treatment, whichever occurs first. The Investigator must follow up on all drug-related AEs, SAEs, and other reportable information until the events have subsided, returned to baseline, the patient has initiated any other anticancer treatment, or in case of permanent impairment, until the condition stabilizes.

All AEs and SAEs must be recorded on source documents and collected in EDC.

Although AEs should be based on the signs or symptoms detected during the physical examination and on clinical evaluation of the patient, a specific diagnosis should be reported as the AE whenever feasible. In addition to the information obtained from those sources, the patient should be asked the following nonspecific question: “How have you been feeling since your last visit?” Signs and symptoms should be recorded using standard medical terminology.

Any unanticipated risks to the patients must be reported by the investigator promptly to the Sponsor and IRB/IEC.

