15.3 Serious Adverse Event Reporting

All SAEs regardless of attribution, other reportable information, and follow-up information must be reported within 1 business day of learning of the event by completing the SAE form and

either emailing or faxing the form to the [SAE Reporting Contact](#). Calithera Biosciences (or designee) will process and evaluate all SAEs as soon as the reports are received. For each SAE received, Calithera Biosciences will make a determination as to whether the criteria for expedited reporting have been met. The Medical Monitor should also be contacted for any fatal or life-threatening SAE that is considered possibly or probably related to study drug.

Calithera Biosciences, Inc. (or designee) is responsible for reporting relevant SAEs to the relevant regulatory authorities and participating Investigators, in accordance with FDA regulations *21 CFR 312.32*, *ICH Guidelines*, *European Clinical Trials Directive (Directive 2001/20/EC)*, and/or local regulatory requirements and monitoring the safety profile of the study drug. To meet this requirement, Calithera Biosciences, Inc. (or designee) may request additional information from the sites including, but not limited to, hospitalization records. Any requests for such information should be addressed in a timely manner. Additionally, any SAE considered by an Investigator to be possibly or probably related to the study therapy that is brought to the attention of the Investigator at any time outside of the time period specified for SAE reporting also must be reported immediately to one of the individuals listed on the [Sponsor contact](#) information page.

Reporting of SAEs by the Investigator to the Institutional Review Board (IRB) or Independent Ethics Committee (IEC) will be done in accordance with the standard operation procedures and policies of the IRB/IEC. Adequate documentation must be maintained showing that the IRB/IEC was properly notified.

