ATTACHMENT 1: SCHEDULE OF STUDY ASSESSMENTS

(1 cycle = 28 days)	Pre-randomization	Post-randomization				
	Screening ¹	Cycle 1		Cycle 2+	Cycle 13+ (Every 3 cycles) ¹³	End of Treatment/ Follow up
Assessments	≤ 21 days prior to CID1	Day 1 ² (≤3 days post randomization)	Day 15 (± 2 days)	Day 1 (± 5 days)	Day 1 (± 7 days)	EOT: Within 28 days post treatment discontinuation
Written Informed Consent	X					
Inclusion/Exclusion Criteria	X					
Demographics and Medical History	X					
Physical Examination ³	X	X	X	X	X	X
Height	X					
Weight	X	X	X	X	X	X
Vital Signs ⁴	X	X	X	X	X	X
Karnofsky Performance Status	X	X		X	X	X
12-lead ECG with QTcF	X					
Urinalysis ⁵	X					
HgA1c levels ^{5, 6}	X					
Triglyceride and total cholesterol levels ^{5, 7}	X			X		
Coagulation tests ⁵	X					
Serum Chemistry levels	X	X	X	X	X	X
Hematology	X	X	X	X	X	X
Serum or Urine Pregnancy Test ⁸	X					X
Pharmacokinetic (PK) Assay ⁹			X	X		
CB-839 or Placebo Dosing		CB-839 or Placebo will be administered twice daily (BID) with food				
Everolimus Dosing		Everolimus will be administered once daily (QD) at the same time every day.				
Optional Tumor Biopsy		Can be collected any time on study. Patients must sign the optional tumor biopsy consent				
Archival Tumor Collection	X					

(1 cycle = 28 days)	Pre-randomization	Post-randomization				
Visit	Screening ¹	Cycle 1		Cycle 2+	Cycle 13+ (Every 3 cycles) ¹³	End of Treatment/ Follow up
Assessments	≤ 21 days prior to C1D1	Day 1 ² (≤3 days post randomization)	Day 15 (± 2 days)	Day 1 (± 5 days)	Day 1 (± 7 days)	EOT: Within 28 days post treatment discontinuation
Radiographic Evaluation of Tumor Burden (diagnostic CT with intravenous contrast or MRI) ¹⁰	X ¹¹			Every 8 weeks	Every 12 weeks	X
Quality of Life Questionnaires		X		X	X	X
Adverse Events		Document new or worsening AEs from time of first dose through 28 days after study treatment discontinuation. AE information will be collected at study visits and may also be collected via any other forms of communication or by subject report. Certain AEs and SAEs that are ongoing 28 days after study discontinuation are to be followed until resolution or determination by the investigator that the event is stable or irreversible.				
Concomitant Medications	Document concomitant medication taken from time of informed consent through 28 days after study treatment discontinuation.					
Follow up						X ¹²

Explanation of Superscripts

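### SAP 8.6.2 runs treatment-emergent status to the clinical cutoff, past the 28-day adverse event window, so selectively captured late events enter the by-arm TEAE tables

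*SAP*

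**What the plan says.** SAP 8.6.2 has two limbs. The first makes an event treatment-emergent if it occurs "on or after the first dose of study drug is administered until the clinical cutoff date". The second covers worsening of conditions already present, and is worded "or existing events that worsened after the first dose during the study". Neither limb has an end tied to the last dose or to new therapy.

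The collection rules end sooner:

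- Protocol 10.6 records events from when the patient "receives the first dose of study drug up to 28 days after the last dose".
- Protocol Attachment 1 instructs sites: "Document new or worsening AEs from time of first dose through 28 days after study treatment discontinuation". SAP Appendix B carries the same instruction.
- Protocol 15.2 follows AEs and SAEs "up to 28 days after the last dose or until the start of a new treatment, whichever occurs first".

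Two rules let later events in. Protocol 15.3 requires a report of any SAE the investigator considers possibly or probably related, even if it comes to notice "at any time outside of the time period specified for SAE reporting". Protocol 15.1 asks for all deaths, including those from progression, to be reported as SAEs, and SAP 8.6.2 says that this is how the study is conducted. SAP 8.6.2 then leaves Grade 5 events in patients who died of progressive disease out of the SAE summaries. It states no such exclusion for the TEAE tables by grade or the Grade 3 and above tables.

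**The concern.** A treatment-emergent window longer than the collection window does no harm if nothing is recorded in the gap. Here something is, but only certain kinds of event: serious and related, fatal, or a worsening of something already under follow-up. Milder or unrelated new events from the same months are missing. The tables would then mix a complete record of the treatment period with a partial, severity-weighted record of what came after.

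The gap need not be equal between arms. If CB-839 delays progression as the design assumes, control patients stop treatment earlier and spend longer in the gap, often on other therapy. Comparing safety between the arms is a stated objective (Protocol 5.0). With about 21 control and 42 experimental patients, one extra patient with an event moves a rate by 1/21 = 4.8 percentage points in the control arm, or 1/42 = 2.4 in the experimental arm.

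**Working it through.** **1. The windows side by side.** All start at first dose.

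| Source | End of window | New therapy ends it? |
|---|---|---|
| SAP 8.6.2, new events | Clinical cutoff | No |
| SAP 8.6.2, worsening | During the study, no date | No |
| Protocol 10.6 | 28 days after last dose | Not stated |
| Protocol Attachment 1 and SAP Appendix B | 28 days after discontinuation | Not stated |
| Protocol 15.2 | 28 days after last dose, or new treatment if earlier | Yes |

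There are two separate conflicts. SAP 8.6.2 disagrees with every collection rule, including the SAP's own schedule. The collection rules also disagree among themselves on new therapy.

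**2. What can be recorded after the window.**

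- Related SAEs, through Protocol 15.3.
- Deaths in survival follow-up, if reported as SAEs (Protocol 15.1, SAP 8.6.2). Progression deaths leave the SAE summaries but not, as written, the other TEAE tables.
- Worsening of events ongoing at day 28, since Attachment 1 has certain of these followed further.
- Events between the start of new therapy and day 28, which Protocol 10.6 and Attachment 1 collect and Protocol 15.2 does not.

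**3. How long the gap is.** The documents give no figure to reproduce, so this is an illustration.

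Inputs from the documents: control median PFS 3.7 months, hazard ratio 0.60 and 8-month accrual (SAP 6.2); cutoff about 20 months from first randomization (SAP 6.3), or 8 + 6 = 14 months if the accrual and follow-up in SAP 6.2 are used; median OS 12.1 months for third-line everolimus (Protocol 9.1).

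Assumptions not in the documents: treatment ends at the PFS event, the 12.1-month OS median applies to both arms, and death does not precede the PFS event. PFS and OS are exponential and entry is uniform.

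The experimental median is 3.7/0.60 = 6.2 months, and 28 days is 28/30.4375 = 0.92 months. For PFS time T, death time D and available follow-up F:

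- nominal SAP window = min(D, F)
- 28-day window = min(T + 0.92, D, F)
- gap = the first minus the second

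Mean months per patient, by simulation:

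| Cutoff | Arm | SAP window | 28-day window | Gap | Gap as share of SAP window |
|---|---|---|---|---|---|
| 20 mo | PboE | 11.46 | 5.71 | 5.75 | 50% |
| 20 mo | CBE | 12.31 | 7.92 | 4.39 | 36% |
| 14 mo | PboE | 8.29 | 5.05 | 3.24 | 39% |
| 14 mo | CBE | 8.70 | 6.37 | 2.33 | 27% |

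Excess gap per control patient: 5.75 − 4.39 = 1.4 months at 20 months, and 3.24 − 2.33 = 0.9 at 14 months.

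Sensitivity to the survival assumption:

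- Ignoring death: 10.1 − 7.9 = 2.2 months at 20 months, and 4.8 − 3.5 = 1.3 at 14.
- OS hazard ratio also 0.60: about 0.2 months at 20 months and 0.5 at 14.

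These are amounts of time, not numbers of events.

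**The case against.** The strongest reply is that a definition can count only what is collected. For routine adverse events the 28-day rule closes the record, and the SAP's cutoff date is then little more than a data-cut limit. That stands, and it is why the shares of time above must not be read as shares of events.

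Second, the late SAEs that must be reported are those judged related, and keeping them in the main table is a defensible, conservative choice. That stands in part. They must stay visible, but a table that takes in only related late events is not a like-for-like comparison of arms.

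Third, SAP 8.6.2 already removes progression deaths from the SAE summaries and lists deaths by arm. This narrows the problem. It leaves deaths from other causes, and progression deaths in the TEAE tables that are not SAE tables.

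A reader might infer three stronger things that the documents do not support:

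- *That off-treatment events are attributed to study drug.* Treatment-emergent is a timing label. Relatedness is a separate four-level investigator grade (Protocol 15.1), and related TEAEs have their own tables (Protocol 14.4).
- *That control patients spend 3 to 4 months longer in the gap.* This comes from subtracting untruncated means: 3.7/ln 2 = 5.34, 5.34/0.60 = 8.90, difference 3.6 months. It ignores staggered entry, the cutoff and death. None of the cases above reaches 3 months.
- *That protocol collection should be cut back to the start of new therapy.* The sections disagree on this, and nothing in them shows that the shorter rule is the intended one.

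**Conclusion.** The inconsistency is real and should be corrected before the safety tables are produced. As written, SAP 8.6.2 would count late, selectively captured events as treatment-emergent in the by-arm tables, against the protocol's collection rules and the SAP's own Appendix B.

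The size is moderate and uncertain. The extra time at risk of this misclassification is about 1.4 months per control patient at a 20-month cutoff and 0.9 at 14 months. Across the survival assumptions tried it ranges from about 0.2 to 2.2 months. The direction depends on the assumed PFS benefit being real. The effect on event counts is not quantified, and should be smaller because few events are collected in that time. The primary PFS analysis is not affected.

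**What to change.** In SAP 8.6.2, end both limbs of the definition at the protocol's collection window: onset or worsening from first dose to 28 days after the last dose of study drug.

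Reconcile Protocol 10.6, 15.2 and Attachment 1, and SAP Appendix B, on whether new anti-cancer therapy ends the window, and carry the answer into the SAP definition. The sponsor has to settle which rule is meant.

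Summarise related SAEs and deaths after the window separately by arm, with progression deaths identified, so that nothing is lost from view.

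The cost is one SAP sentence, one added summary and a protocol alignment, with no new data. The one drawback is that late related SAEs leave the main TEAE table, which the separate summary offsets.
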